Blinding will be involved in this study. The primary investigator, study participants, and team members involved in serum/urine end point analyses will be blinded to treatment arm. The investigational pharmacy is responsible for study group assignment and is not blinded. The study team member involved in the fecal bacterial genome analysis will not be blinded, as knowledge of treatment arm will be necessary for the accurate assessment of changes in fecal microbiome composition among study participants.

3. State the maximum number of subjects to be enrolled in each group. Include power calculations to explain what can be studied with the proposed sample size and specify the statistical tests that will be used to test **each** hypothesis. If the research project needs to be pilot tested, state how many subjects will be enrolled in the pilot test and how the procedures for the pilot test will differ from those used in the research protocol.

There will be a total of 30 subjects enrolled; 15 participants will receive Rifaxmin and 15 will receive placebo.

D. Subject Criteria (See Vulnerable Populations appendix, if applicable): Include age range, gender, disease, and stage of treatment. Justify excluding subjects based on race or

gender (including child-bearing potential for women), age (children), or non-English speakers.

- 1. Inclusion criteria: State the criteria for inclusion in the study in a specific and detailed manner.
 - Patients 18 years of age or older
 - Stage IV-V chronic kidney disease (eGFR ≤ 39 ml/min/1.73m²)
- 2. Exclusion criteria: State the criteria for excluding potential subjects from the study in a specific and detailed manner.
 - Patients with normal renal function or those with less advanced kidney disease
 - Inability or unwillingness to provide consent
 - Patients undergoing hemodialysis or peritoneal dialysis therapy or those who have undergone organ transplant
 - Patients who may be pregnant
 - Hemodynamically unstable patients
 - Patients with liver failure, pancreatic insufficiency, or inflammatory bowel disease
 - Patients with ongoing or recent infection and those with history of C-diff infection
 - Patients with abnormal bowel structure secondary to surgical or anatomic variations
 - Patients on certain medications including immunosuppressants, antidiarrheal agents, and current or recent (within the last 2 months) use of antibiotics

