Blood, urine and stool samples will be labeled with study information and by the subjects' unique study ID. They will be analyzed in the lab of [name] and the lab of [name] at the University of Pittsburgh Medical Center. Additional serum and urine samples will be stored in a -80°C freezer in [name] lab for those patients consenting for sample storage.

5. Timeline: Consider attaching a study flow chart illustrating subject visits and tests or procedures to be performed at each visit **and/or** include a chart or graph format that reflects the project activities and anticipated time frame of completion.

Day 0 (baseline visit): Consented participants will have an initial appointment dedicated to the collection of baseline samples and study medication will be dispensed at this visit. Complete review of the patient's history and physical examination will be recorded. All study participants will continue receive standard of care treatment for their chronic kidney disease. Study participants will be provided with a 10-day course of Rifaximin. A medical history will be obtained, including current medications, comorbid conditions, lifestyle indicators (such as tobacco and alcohol use), review of recent laboratory studies (such as BMP, CBC, and lipids); this information will be recorded and stored on all study participants. Serum, urine and fecal samples will be collected at this

visit. On Day 1, study participants will begin Rifaximin 550mg PO BID or placebo for a total of ten days duration.

Day 11 (post-therapy follow-up visit): Study participants will provide stool samples within 24 hours of their last dose of Rifaximin or placebo. Serum and urine samples will be drawn at this study visit. Vital signs will be checked and a brief interview will be conducted to assess for any potential adverse reactions to the study medication. Follow up visits can be arranged at the patient's request if needed.

Day 25 (steady state follow-up visit): Study participants will provide stool samples. Serum and urine samples will be drawn at this study visit. Vital signs will be checked and a brief interview will be conducted to assess any recent health changes.

- **F. Risk/benefit assessment:** As appropriate, address the following parameters as each relates to the individual subject in the study. Be sure to include consideration of study assignment (Arm A, Arm B, placebo, active substance, etc):

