- 1. Physical risk: Rifaximin has known potential side effects. Since this medication has primarily been studied in patients with advanced liver disease, it is unclear which of these side effects are unique to this population of patients. The most common side effects reported in patients with liver disease included peripheral edema, ascites, nausea, dizziness, fatigue, headache, muscle spasms, pruritus, abdominal pain, and rash. Most common side effects in patients without liver disease are believed to be gastrointestinal in nature; mainly including nausea, abdominal pain/bloating, and diarrhea. Serious reactions have been reported by the manufacturer with this therapy, including superinfection with clostridium difficile, hypersensitivity reaction, angioedema, anaphylaxis, and exfoliative dermatitis. The risks associated with venipuncture in order to obtain blood samples carries a small risk of excessive bleeding, vasovagal syncope, hematoma/infection at the site of vein puncture, and potentially multiple punctures in order to locate veins.
- 2. Psychological risk: No anticipated risk.
- 3. Social risk: No anticipated risk.
- 4. Economic risk: Low anticipated risk. The patient will have no cost associated with the study. In the instance of an adverse event, normal medical treatment should be sought and insurance billed as is standard.
- 5. Potential benefit of participating in the study:
 - a. To the individual subject and/or parent if any: Individuals are not expected to benefit directly from participation in this study.
 - b. To the population from which the subject is drawn: This study may provide critical insight into understanding the altered metabolism of TMAO in CKD and provide preliminary evidence to support the development of future large-scale studies.
 - c. To science, society, and humanity in general: This may lead to development of interventions which could decrease the burden of cardiovascular disease in patients with chronic kidney disease, ultimately reducing health care costs and outcomes for patients with these conditions.
- **G. Location where study will be performed:** Indicate where all portions of the study will take place and where the research subject's records will be kept.

This study will be conducted at the University of Kansas Hospital with patients being recruited from the outpatient nephrology clinics. Records will be kept on secure spreadsheets that can only be accessed by the study team.

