- 1. Please note that any study proposal with more than minimal risk must include a data and safety monitoring plan. Elements of the plan include:
 - a. Persons/groups who will review the data (study team; independent safety monitor, data monitoring committee or formal DSMB)
 The study team
 - b. Data/events that will be reviewed
 Adverse reactions, early discontinuation, tolerance and side effects.
 - c. Frequency of review

 After ten days of therapy and PRN.
 - d. Types of analyses to be performed Patient interview
 - e. Safety-related triggers that would cause the PI to stop or alter the study Multiple adverse reactions may lead the team to reconsider the dose or the chosen agent.
- 2. Describe how adverse events and unanticipated problems will be ascertained and handled. Explain exactly which type of problems will be considered serious and reported to the IRB. The reporting timeframe should also be detailed.

Participants will be given contact information for KU nephrology on-call numbers. There have been rare serious adverse medication reactions with Rifaximin, including intestinal

superinfection, C-diff associated diarrhea, angioedema, or exfoliative dermatitis. In these instances a patient will be instructed to seek emergency medical attention.

3. Explain exactly what will happen if a patient experiences an adverse event or other problem (for example, will discontinue study participation).

Patients will be asked to report any adverse reaction. They will be given the contact information for the nephrology nursing line who can contact a member of the study team. This is a short study lasting 25 days and patients will have 3 total study visits, on day 0, day 11, and day 25.

III. Subject Participation

A. Recruitment:

1. Describe locations from which the subjects will be recruited and what arrangements have been made with other institutions (if applicable).

The initial contact will occur at KU nephrology clinic. There will not be outside institutions involved.

2. Describe by whom and how the recruitment is conducted.

A subject's primary treatment team will be the initial contact to gauge interest in learning about the study. From there a member of the study team will discuss the study in further detail.

3. Attach a copy of advertisements and/or flyers and state where they will be placed.

There will not be advertisements or flyers.

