4. Attach a copy of the recruitment letter or introductory statement and describe planned use or distribution of the document.

There will not be a recruitment letter.

B. Screening Interview/questionnaire: If an interview or questionnaire will be used for screening, attach a copy and indicate where, how, and who will conduct the interviews and their qualifications. Address how consent to participate in the screening process will be obtained.

Clinic patients will be screened for inclusion and exclusion criteria. If they are appropriate for inclusion in the study they will be approached by their clinical nephrology team members who will assess their interest and willingness to participate in the study. If they are interested in participation a member of the study team will discuss the study in further detail.

C. Informed consent process and timing of obtaining of consent

1 Indicate who will give subjects detailed and comprehensive information about the study and obtain their written consent.

A member of the study team as outlined above.

2 Indicate how the consenting process will be structured to ensure independent and thoughtful decision-making, and what steps will be taken to avoid coercion and guarantee confidentiality.

Clinic patients will be screened in advance for inclusion and exclusion criteria. During their clinic visit with their clinical nephrologist, their doctor will ask if they are interested in participating in the study. If the patient expresses interest, a member of the study team will discuss the project with the patient. The consent may be obtained at that clinical visit if time permits for full explanation and patient is agreeable. Alternatively they may take the consent form home for review and a study visit will be arranged at a separate time and location.

Indicate how, and by whom, it will be determined whether the subject is able to give informed consent, or whether their legal guardian will give informed consent. For subjects whose ability to give informed consent may be compromised by cognitive and/or decisional impairment (examples may include individuals with a psychiatric disorder, an organic impairment, a developmental disorder, or those suffering from a terminal illness, degenerative disease, severe physical handicap or dependence on drugs or alcohol), complete Appendix I.

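### The exclusion list does not address known hypersensitivity to the study drug, although the protocol names hypersensitivity, angioedema and anaphylaxis among its serious reactions

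*Combined protocol and SAP*

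**What the plan says.** **Eligibility (II.D.1 and II.D.2).** There are two inclusion criteria, age and CKD stage, and nine exclusion items. The item closest to the drug's named risks is "Patients with ongoing or recent infection and those with history of C-diff infection". The item closest to drug history is "Patients on certain medications including immunosuppressants, antidiarrheal agents, and current or recent (within the last 2 months) use of antibiotics".

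**Risks (II.F.1).** The protocol states: "Serious reactions have been reported by the manufacturer with this therapy, including superinfection with clostridium difficile, hypersensitivity reaction, angioedema, anaphylaxis, and exfoliative dermatitis".

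**Data and safety monitoring plan, item 2.** This section says "There have been rare serious adverse medication reactions with Rifaximin" and includes among them "superinfection, C-diff associated diarrhea, angioedema, or exfoliative dermatitis".

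**Screening (III.B).** "Clinic patients will be screened for inclusion and exclusion criteria".

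**Day 0 (II.E.5).** A full history review and a physical examination are recorded. The itemised content begins "A medical history will be obtained, including current medications, comorbid conditions, lifestyle indicators (such as tobacco and alcohol use" and continues with recent laboratory results.

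**Termination (II.D.3).** The investigator may end participation if the subject turns out not to satisfy the inclusion or exclusion criteria.

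**The concern.** The protocol identifies serious allergic-type reactions to rifaximin but has no eligibility rule for a patient already known to have had one. A coordinator who follows the written criteria exactly would find such a patient eligible.

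This is a matter of participant safety. Treatment is double-blind (II.B), and II.F.5 expects no direct benefit to the individual. A risk that can be foreseen and found by asking one question is hard to leave uncovered in that setting. The scheduled visits are Days 0, 11 and 25 and dosing begins on Day 1, so the first scheduled visit after the first dose falls after the ten-day course has ended.

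**Working it through.** No arithmetic applies. The check compares the named serious reactions with the eligibility rules, then looks for any other written safeguard.

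**Step 1. Named reactions against the eligibility criteria.**

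| Serious reaction | II.F.1 | Monitoring plan, item 2 | Matching history-based exclusion in II.D.2 |
|---|---|---|---|
| C. difficile superinfection | yes | yes | yes (prior C. difficile) |
| Hypersensitivity reaction | yes | no | none |
| Angioedema | yes | yes | none |
| Anaphylaxis | yes | no | none |
| Exfoliative dermatitis | yes | yes | none |

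None of the nine exclusion items and neither of the two inclusion criteria mentions allergy, hypersensitivity, intolerance or contraindication. II.D.2 also has no exclusion at the investigator's discretion that could serve instead.

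**Step 2. Does the antibiotic item cover it?** No. It is an exposure window of two months. A patient who reacted to rifaximin a year ago and has taken no antibiotic since would pass it.

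**Step 3. Does another section close the gap?**
- Screening (III.B) applies the inclusion and exclusion criteria and adds nothing to them.
- Termination (II.D.3) refers back to the same criteria, so an allergy discovered after enrolment would not trigger it.
- The Day 0 history (II.E.5) itemises medications, comorbid conditions, lifestyle and laboratory results. Drug allergy is not named, and no finding from the history is linked to eligibility.
- The investigational pharmacy (II.C.2) assigns the group and is unblinded, but it is given no allergy check.

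**Step 4. Could the criterion be in text that was not available?** The material reviewed lacks some text between II.G (study location) and the data and safety monitoring plan. The eligibility list runs without a break into II.D.3, so a missing exclusion item there is unlikely.

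**Result.** Followed as written, the eligibility rules admit a patient with a known reaction to rifaximin.

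**The case against.** The strongest reply is that the practical exposure is small, and most of that reply stands.

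- The Day 0 review of history is described as complete, and its itemised list is introduced as examples, so an allergy may well come to light before drug is dispensed. Patients are also approached by their own nephrology team. This lowers the likelihood, but no written rule says what to do with the finding.
- Known rifaximin hypersensitivity normally implies earlier exposure. I.C gives the approved use as hepatic encephalopathy in end-stage liver disease, and II.D.2 excludes liver failure and recent antibiotic use. This narrows the group but does not empty it: I.C also mentions traveler's diarrhea, and remote exposure remains possible.
- With 1:1 allocation, such a patient would have an even chance of receiving placebo.

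A reader might also infer four stronger points, which the documents do not support.

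- *That the risk section and the exclusion list contradict each other.* One lists what may happen on treatment and the other lists who may enrol. Nothing says that each risk must produce an exclusion, or that the C. difficile item was derived from the risk list. This is an omission.
- *That primary outcome data would be lost.* No text says that a reaction ends dosing or Day 11 sampling. If one patient were lost, 15 − 1 = 14 would remain in the active arm, still above the 13 that II.C.1 says are needed.
- *That patients are without support until Day 11.* The monitoring plan provides on-call numbers, a nursing line, review as needed and an instruction to seek emergency care, and II.E.5 allows extra visits on request. The protocol also does not state where the first dose is taken.
- *That the gap extends to related antibiotics.* The documents name no drug class and say nothing on cross-reactivity, so the point rests on rifaximin itself.

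**Conclusion.** The omission is real. As the criteria stand, a patient with known hypersensitivity to rifaximin is eligible for blinded dosing, and no other written provision acts on that history. The likelihood is low and cannot be estimated, because the documents give no prevalence of known allergy. The possible consequence, on the protocol's own list, includes anaphylaxis.

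This is an eligibility and safety gap. It is not a statistical error and leaves the sample size and the analysis unchanged. The conclusion assumes that eligibility is decided on the written criteria, as III.B and II.D.3 indicate, and that the text not available contains no further exclusion item.

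**What to change.** Reconcile II.D.2 with the serious reactions named in II.F.1 and in item 2 of the data and safety monitoring plan, so that known hypersensitivity to the study medication is addressed at eligibility. The sponsor should set the exact wording and scope. Because screening and termination already refer to the listed criteria, a change in II.D.2 carries through to both without further edits.

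Add drug allergies to the items recorded in the Day 0 history in II.E.5, so that the information needed to apply the criterion is collected before study medication is dispensed.

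The cost is one criterion and one history item at a visit that already takes a history. Almost no eligible patients would be lost.

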- In mice they found that chronic supplementation with L-carnitine resulted in alteration of cecal microbial composition, enhanced synthesis of TMAO, and increased atherosclerosis but not when intestinal microbiota were suppressed.

Tang WH, et al. Intestinal Microbial Metabolism of Phosphatidylchline and Cardiovascular Risk. *New England Journal of Medicine* 2014.

- Plasma and urinary levels of TMAO and plasma choline and betaine levels were
 measured by liquid chromatography and online tandem mass spectrometry after
 they administered a phosphatidylcholine challenge in 40 healthy participants.
 There were time dependent increases in serum TMAO levels and its D9 labelled
 isotopologue as well as other choline metabolites after the phosphatydlcholine
 challenge. The levels were also assessed before and after suppression of bowel
 flora by use of oral broad spectrum antibiotics (metronidazole 500 mg BID plus
 Ciprofloxacin 500 mg daily for 1 week) in 6 of the participants. Plasma levels were
 suppressed after administration of antibiotics but returned after withdrawal of
 antibiotics.
- They examined the relationship between fasting serum TMAO level and the incidence of major adverse cardiovascular events (death, MI, or stroke) during 3 years of follow up in 4007 patients who underwent elective coronary angiography. Elevated serum TMAO level predicted increased risk of a major adverse cardiovascular outcome after adjusting for traditional risk factors.

[name], et al. Manuscript currently under consideration

- In order to assess TMAO levels in CKD a cross-sectional study was undertaken in a group of patients with variable degress of chronic kidney disease ranging from normal to ESRD (n=104). We observed a graded rise in serum TMAO that corresponded to increasing CKD severity. The median concentrations in dialysisdependent patients was approximately 30 times higher than in control patients (94.4 μM in ESRD compared to 3.3 μM in Controls, P<0.001).

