in rodents and was found to be strongly associated with the incidence of cardiovascular events in humans (2-5). In normal physiologic conditions, circulating TMAO is rapidly removed from circulation primarily by excretion into the urine (7). We previously postulated that TMAO levels would be substantially elevated in patients with CKD, and to test this hypothesis we performed a cross-sectional analysis of serum TMAO concentrations in a cohort of patients with varying levels of CKD and normal healthy controls. In this study, we observed serum TMAO concentrations become markedly elevated in the advanced stages of CKD, with end-stage renal disease (ESRD) patients exhibiting mean levels 30-fold higher than healthy controls.

If TMAO contributes to atherosclerosis formation in CKD patients, therapeutic interventions to reduce TMAO production may represent a method to reduce cardiovascular morbidity and mortality in this population. Prior studies suggest that short-term suppression of gut flora with antibiotics dramatically decreased TMAO levels in patients with normal kidney function (5); however, this approach has not yet been tested in patients with CKD that exhibit much higher serum levels of TMAO.

Rifaximin is a novel antibiotic that is currently approved for treatment of hepatic encephalopathy in patients with end-stage liver disease. Rifaximin demonstrates little systemic absorption, with 97% of the parent drug being excreted unchanged in the feces (9). Its primary use is to target pathogenic intestinal bacteria in various disease states , including cirrhosis and traveler's diarrhea. In this study we seek to evaluate whether Rifaximin will decrease levels of TMAO in patients with advanced kidney disease and to study the effects of Rifaximin on the intestinal microbiome of patients with CKD.

Explain how the performance of this proposed project will advance our knowledge in this field, and/or improve our understanding of the disease or physiological condition being studied.

This study will determine if elevated levels of TMAO in CKD are at least partially dependent on the presence of certain intestinal flora and if serum TMAO levels are modifiable by therapy with Rifaximin.

3. Explain how this study might improve the diagnosis or treatment of the disease being studied (if applicable), or advance knowledge in the field.

This will provide preliminary evidence to support the intestinal flora as a target for reducing TMAO levels in CKD patients.

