- 3. Withdrawal/Termination criteria: Include the specific circumstances in which the subject's participation will be terminated by the investigator. Include any necessary safety precautions to be applied to those who withdraw (tapering drug doses, evaluative x-ray, etc.)
 - Participation may be terminated if subject is found to not meet the inclusion or exclusion criteria. Participants may withdraw at any time.
- 4. Clarify whether a study subject may participate in another research study while participating in this research study.
 - Patients should not participate in another research study while taking the study medication but exceptions may be made dependent on the nature of the other research study.

E. Specific methods and techniques used throughout the study

1. Laboratory tests: Methods for collecting specimens and data. Indicate purpose, amount and timing of tests performed (e.g., blood tests, urine tests, CSF tests, EKGs, etc.). Include specific test components and estimated volume and type of specimens needed for each test.

Serum and urine samples (30ml each) will be collected at the baseline and post-therapy visits (day 0, day 11, and day 25) for measurement of TMAO, endotoxin, IL-6, IL-8, and TNFa levels. Fecal specimens will be collected at these same time points in order to assess changes in the intestinal microbiome after administration of Rifaximin.

2. Study Procedures: Describe each procedure to be used in the study, including the instruments used, time required for each procedure, cognitive assessments, etc.

Blood, urine and stool samples will be collected for analysis. Aside from venipuncture there will be no other procedures.

3. Clearly indicate which procedures, tests, visits, etc., are parts of usual standard therapy and which are performed solely for research purposes. Make it clear which tests are routinely performed for clinical care but are providing data for the research (and are billable to insurance companies), and which tests are only performed for research purposes (not billable to insurance companies).

Any samples collected during the specified research appointments will be used for research purposes only and will not be billed.

4. Describe the fate of any body component (blood, CSF, bone marrow, etc.) used in the study, emphasizing confidentiality of labeling of the sample and the sample's destruction or storage.

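### No kidney-function marker is scheduled with the TMAO samples (none at Day 11 or Day 25), so a change in serum TMAO cannot be divided between gut production and renal clearance

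*Combined protocol and SAP*

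**What the plan says.** **What is measured.** Section II.E.1 gives the schedule and the analytes together: serum and urine are taken at Days 0, 11 and 25 "for measurement of TMAO, endotoxin, IL-6, IL-8, and TNFa levels". Stool is collected at the same visits for the microbiome. Section II.E.2 adds that "Aside from venipuncture there will be no other procedures".

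**What is known about the kidney at each visit.**
- Day 0: Section II.D.1 requires an eGFR of 39 or below for entry, without naming a source or date. Section II.E.5 adds a medical history that includes "review of recent laboratory studies (such as BMP, CBC, and lipids"; these results are recorded, but they come from the chart and not from the Day 0 draw.
- Day 11 (Section II.E.5), apart from samples: "Vital signs will be checked and a brief interview will be conducted to assess for any potential adverse reactions to the study medication".
- Day 25 (Section II.E.5), apart from samples: "Vital signs will be checked and a brief interview will be conducted to assess any recent health changes".

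**What the background says about TMAO.** Section I.C.1 states that in normal physiology "circulating TMAO is rapidly removed from circulation primarily by excretion into the urine". Section I.B.3 reports from the team's own cross-sectional study: "We observed a graded rise in serum TMAO that corresponded to increasing CKD severity", with medians of 94.4 μM in ESRD and 3.3 μM in controls.

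**What the study wants to conclude.** The hypothesis in Section I.A is that rifaximin suppresses the flora that generate the TMAO precursor. Section I.C says the study will show whether raised TMAO in CKD depends at least in part on intestinal flora, and whether serum levels can be modified by rifaximin. The primary objective in Section II.A concerns serum TMAO itself. The design is randomised 1:1, placebo-controlled and double-blind (Sections II.B and II.C.1), but the only test named, in Section V.A, is a two-sided paired t-test of values before and after treatment.

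**The concern.** Serum TMAO reflects two processes: how much precursor the gut produces and how fast the kidney clears the product. The background describes both, and in this population the second is impaired. The hypothesis concerns only the first. With no renal marker taken alongside TMAO after baseline, an observed change cannot be assigned to one or the other.

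Two things are at stake. The first is mechanism. If treatment itself altered kidney function, the resulting TMAO change would be part of the between-arm difference, and randomisation would not remove it. Section II.F.1 lists nausea and diarrhea among the common side effects in patients without liver disease. Fluid loss lowering GFR in advanced CKD is a plausible route, but that is an inference and not something the documents state. Such a change could hide a true fall in production, leaving a null result hard to read. The second is the named paired test, which does not use the placebo arm and so takes any common drift in clearance as a treatment response.

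The gap may not be repairable later. Section IV.B says samples are destroyed after testing unless the participant has consented to storage.

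**Working it through.** **Inputs from the documents.** Mean change −30%, SD 30%, 90% power, type I error 0.05, stated n = 13, 15 per arm (Section II.C.1); two-sided paired t-test (Section V.A); 94.4 and 3.3 μM (Section I.B.3).

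**Inputs assumed.** The size of any GFR change, and the model serum TMAO ∝ production / GFR at steady state. The documents give neither.

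1. *The plan's own sample size.* Standardised effect 30/30 = 1.0. With the noncentral t distribution, a two-sided paired test has 88.3% power at n = 12 and 91.1% at n = 13. The stated 13 is reproduced; n = 15 gives 94.9%. The figure is correct for a paired test within one arm.

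2. *Size of the kidney's influence.* 94.4 / 3.3 = 28.6-fold between ESRD and controls. This is a cross-sectional contrast between extremes. It shows that kidney function matters, not how much it moves in 11 days.

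3. *Effect of a GFR change with production unchanged.*

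| GFR change | Serum TMAO change |
|---|---|
| −10% | 1/0.90 − 1 = +11.1% |
| −20% | 1/0.80 − 1 = +25.0% |
| +10% | 1/1.10 − 1 = −9.1% |
| +20% | 1/1.20 − 1 = −16.7% |

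4. *Masking.* Production falls 30% and GFR falls 20%: 0.70 / 0.80 = 0.875, an observed change of −12.5%.

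5. *Imitation.* To produce −30% with production unchanged, GFR must rise by 1/0.70 − 1 = 43%.

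6. *Common drift and the paired test.* Take no drug effect, SD 30% and n = 15. A mean TMAO drift of 5%, 10% or 15%, from whatever cause, makes the paired test reject in 9.2%, 22.5% or 43.8% of trials instead of 5%. If the same drift occurs in both arms, a between-arm test of change stays at 5%.

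7. *Chance imbalance between arms.* If clearance-driven change has an SD of 10 or 15 points, its between-arm SE is 10 × √(2/15) = 3.7 or 15 × √(2/15) = 5.5. The full between-arm SE at SD 30 is 30 × √(2/15) = 10.95. If the clearance component is part of the planned SD, it contributes 10²/30² = 11% or 15²/30² = 25% of the variance, already included in that 10.95.

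**The case against.** The strongest reply is that the placebo arm does this job. Clearance changes unrelated to treatment are balanced in expectation, so comparing change between arms estimates rifaximin's effect on serum TMAO without any creatinine. That effect is the stated primary objective. This stands. A reader might infer that a clearance change cannot be separated from a rifaximin effect at all, or that the trial cannot show serum TMAO to be modifiable; the randomised design in Sections II.B and II.C.1 supports neither inference. The exposure to common drift comes from the choice of a paired test in Section V.A.

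Three further stronger readings also fail.
- Chance imbalance in kidney function is not an additional bias: step 7 shows it is already inside the between-arm standard error if it is part of the planned SD.
- Baseline kidney data are not absent: there is an entry eGFR and a recorded chart review. They are undated and not drawn with the TMAO sample, but they exist.
- The documents do not show that these patients have unstable kidney function over 11 days. They come from outpatient clinics (Section II.G), and Section II.D.2 excludes hemodynamic instability, ongoing or recent infection, and dialysis. No stability requirement for eGFR is stated, but no rate of change is given either.

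It can also be said that the mechanistic claim is hedged, that this is a pilot, and that stool microbiome data will help. All true, but composition data do not measure TMAO clearance. Nor does urine TMAO fill the gap, since no timed collection or urine creatinine is described.

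**Conclusion.** The gap is real and its consequence is limited. No renal marker accompanies the TMAO samples, and none exists at Day 11 or Day 25. The trial therefore cannot say how much of a TMAO change reflects gut production and how much reflects clearance, which weakens the intended conclusion about intestinal flora. A clearance change caused by treatment could mask or distort the effect; a GFR rise of about 43% would be needed to account for the whole planned reduction, so distortion is easier to envisage than outright imitation.

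The percentages rest on serum TMAO being proportional to production over GFR and on assumed GFR changes. The absence of a renal marker rests on the assay list and visit schedule alone and needs neither assumption. The validity of a between-arm estimate of the effect on serum TMAO is not in question. This is a worthwhile, inexpensive improvement, not a flaw that invalidates the trial.

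**What to change.** Add serum creatinine, with calculated eGFR, to the assays in Section II.E.1 at Days 0, 11 and 25, and run it before any sample is destroyed under Section IV.B. Use the Day 0 value as baseline eGFR in place of the undated chart value. In Section V.A, state that eGFR change will be reported by arm beside a between-arm comparison of TMAO change, which also removes the exposure to common drift.

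If an analysis of TMAO change adjusted for eGFR change over the same interval is wanted, label it exploratory. It conditions on a post-randomisation variable that treatment could affect, so it should not be the primary model.

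The cost is about 30 × 3 = 90 routine assays on blood already drawn and one added descriptive analysis, with no extra visit or venipuncture.
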